3.4. Randomization and Unblinding

This is a nonrandomized, open-label study.

4. SELECTION OF STUDY POPULATION

Eligibility will be based on assessments performed prior to receiving study drug on Day 1 in this study.

A participant will be considered to be enrolled after signing of the informed consent form (ICF) and/or the assent form for this study. Informed consent/assent must be properly executed prior to the performance of any protocol-required assessment or procedure.

4.1. Inclusion Criteria

Participants who meet all of the following criteria will be eligible for study enrollment:

1. Male or female participant with SCD who participated and received study drug in a GBT-sponsored voxelotor clinical study

Note: Participants who discontinued study drug due to an AE, but who remained on study, may be eligible for treatment in this study provided the AE does not pose a risk for treatment with voxelotor.

Note: Participants who discontinued Study GBT440-032 as a result of an abnormal transcranial Doppler (TCD) flow velocity assessment (≥ 200 cm/sec) are eligible for treatment in this study.

2. Female participant of childbearing potential is required to have a negative urine pregnancy test prior to dosing on Day 1.

Note: Female participants who become childbearing during the study must be willing to have a negative urine pregnancy test to remain in the study.

- 3. If sexually active, female participant of childbearing potential must use highly effective methods of contraception until 30 days after the last dose of study drug. If sexually active, male participant must use barrier methods of contraception until 30 days after the last dose of study drug.
- 4. Participant has provided written consent/assent (for pediatric participants, both the consent of the participant's legal representative or legal guardian and the participant's assent [where applicable] must be obtained).

4.2. Exclusion Criteria

Participants meeting any of the following exclusion criteria will not be eligible for study enrollment:

- 1. Female participant who is breastfeeding or pregnant
- 2. Participant withdrew consent from a GBT-sponsored voxelotor clinical study
- 3. Participant was lost to follow-up from a GBT-sponsored voxelotor clinical study
- 4. Participant has any medical, psychological, safety, or behavioral conditions that, in the opinion of the investigator, may confound safety interpretation, interfere with compliance, or preclude informed consent
- 5. Active symptomatic coronavirus disease of 2019 (COVID-19) infection
- 6. Known hypersensitivity to voxelotor or any other components of the study drug
- 7. Use of St. John's wort, sensitive cytochrome P450 (CYP) 3A4 substrates with a narrow therapeutic index, or moderate or strong CYP3A4 inducers within 30 days of Day 1

5. TREATMENTS ADMINISTERED

5.1. Treatments Administered

All participants will receive voxelotor QD, administered orally as tablets, dispersible tablets, or a powder for oral suspension dosage form (packaged as stick packs).

Participants aged \geq 12 years will receive a voxelotor dose of 1500 mg QD administered as 3×500 mg tablets regardless of their body weight.

Participants aged < 12 years will receive a voxelotor dose based on their body weight to provide exposure corresponding to the adult dose of 1500 mg QD. The participant's weight at study entry will be used to determine their starting voxelotor dose in this study, as indicated in Table 1 and Table 2. The dose should be adjusted if the participant's weight increases or decreases at a scheduled clinic visit. The participant's weight will be measured according to the Schedule of Assessments (Appendix A), and dose adjustments made as needed and as indicated in Table 1 and Table 2.

The 1500 mg-equivalent dose in participants aged < 12 years will be administered as powder for oral suspension or as dispersible tablets based on the availability of each formulation.

A bioequivalence study in healthy volunteers (Study GBT-0119) comparing the voxelotor powder for oral suspension and dispersible tablet dosage forms showed that a single dose of the powder for oral suspension had an approximately 35% greater exposure than the same mg dose of dispersible tablets. Therefore, for all participants taking dispersible tablets in this study, the dose of the dispersible tablets will be increased by approximately 35%. This increase allows for a dose adjustment for the dispersible tablets ensuring that all participants taking the dispersible tablet dosage form receive the same exposure as participants receiving the powder for oral suspension dosage form (Table 1 and Table 2).

All participants < 12 years of age will receive the doses shown in Table 1 until sites are instructed by the Sponsor to switch these participants to the modified dispersible tablet doses shown in Table 2 at their next regularly scheduled visit (Appendix A). The date of the switch will be recorded on the dosing electronic case report form (eCRF).

Table 1: Voxelotor (Powder for Oral Suspension or Dispersible Tablet) Weight-Based Doses for Participants Less than 12 Years of Age

Weight	1500 mg-Equivalent Adult Dose
5 to < 10 kg	400 mg
10 to < 20 kg	600 mg
20 to < 40 kg	900 mg
≥ 40 kg ^a	1500 mg

Note: All participants ≥ 12 years of age will take voxelotor 1500 mg administered as tablets, regardless of their weight.

^a Voxelotor will be administered as 500 mg tablets.

Table 2: Modified Dispersible Tablet Voxelotor Weight-Based Doses for Participants Less than 12 Years of Age

Population	1500 mg-Equivalent Adult Dose
5 to < 10 kg	500 mg
10 to < 20 kg	800 mg
20 to < 40 kg	1200 mg

Note: All participants ≥ 12 years of age will take voxelotor 1500 mg administered as tablets, regardless of their weight. All participants ≤ 12 years of age and ≥ 40 kg will take voxelotor 1500 mg administered as tablets.

Participants receiving a voxelotor dose of 1500 mg QD, regardless of age or weight, will receive tablets.

All dosage forms of voxelotor may be taken with or without food. Voxelotor tablets should be swallowed whole. Voxelotor dispersible tablets should be dispersed in liquid. Likewise, the powder for oral suspension dosage form should be mixed with liquid. Details regarding preparation of voxelotor for administration are provided in the Pharmacy Manual (provided separately).

Detailed instructions for study drug administration will be provided to participants and their caregivers/legal guardians, as needed.

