5.1.2. Dose Modification

Participants should adhere to the dose level assigned to them.

For AEs that affect safety and tolerability, a trial of reducing or holding the dose may be used. All instances of study drug dose modification (dose reduction, interruption, or discontinuation) should be documented in the participants' medical record and recorded on the eCRF. If the condition/event leading to the dose modification has resolved, the original dose level should be resumed, unless in the judgment of the Investigator this cannot be done safely. Dose reductions due to AEs are provided in Table 3 for participants < 12 years of age and Table 5 for participants ≥ 12 years of age.

When participants switch to the modified dose of dispersible tablet, they will be asked to report any AEs to the clinical site, regardless of when the event occurs relative to the first day of switching to the modified dose. The investigator will determine, based on the participant's reporting of the event, whether a dose decrease is warranted.

Participants with a dose decrease due to an AE should be contacted by the site every 7 days (\pm 2 days) for follow-up of the AE until the new dose is deemed tolerable; at which time the Investigator may attempt to return to the prior dose or maintain the participant at the lowered dose.

Table 3: Weight-Based Dose Reductions for Participants < 12 years of Age Receiving Voxelotor Powder for Oral Suspension

Weight	Voxelotor 1500 mg Dose Equivalent	Dose Reduction 1 New Dose	Dose Reduction 2 New Dose
5 to < 10 kg	400 mg	300 mg	NA
10 to < 20 kg	600 mg	400 mg	300 mg
20 to < 40 kg	900 mg	600 mg	400 mg
\geq 40 kg $^{\rm a}$	1500 mg	1000 mg	500 mg

Abbreviations: NA, not applicable.

Note: All participants \geq 12 years of age will take voxelotor 1500 mg administered as tablets, regardless of their weight.

Table 4: Weight-Based Dose Reductions for Participants < 12 Years of Age Receiving Voxelotor Dispersible Tablet

Weight	Voxelotor 1500 mg Dose Equivalent	Dose Reduction 1 New Dose	Dose Reduction 2 New Dose
5 to < 10 kg	500 mg	300 mg	200 mg
10 to < 20 kg	800 mg	500 mg	300 mg
20 to < 40 kg	1200 mg	900 mg	300 mg
≥ 40 kg ^a	1500 mg	1000 mg	500 mg

Note: All participants ≥ 12 years of age will take voxelotor 1500 mg administered as tablets, regardless of their weight.

Table 5: Dose Reductions for Participants ≥ 12 years of Age Receiving Voxelotor Tablets

Initial Dose	Dose Reduction 1 New Dose	Dose Reduction 2 New Dose

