6.7. Vital Signs

Vital signs (blood pressure and heart rate) will be measured at the time points indicated in the Schedule of Assessments (Appendix A), after the participant has rested comfortably for at least 5 minutes in the supine or sitting position, as age-appropriate and feasible. If the first vital sign measurement is outside the normal range and deemed clinically significant, the measurement will be repeated within 5 minutes.

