Appendix A. SCHEDULE OF ASSESSMENTS

Study Day/Week	Treatment Period								EOS
	First 48 Weeks					After Week 48			+7 days c
	Day 1 a	Week 12 b ± 5 days	Week 24 ± 10 days	Week 36 b ± 10 days	Week 48 ± 10 days	Q12Wk ± 10 days	Q24 Wk ± 10 days	Q48 Wk ± 10 days	
Informed Consent/Assent	X								
Review Inclusion/Exclusion Criteria	X								
Medical History	X								
Weight and Height d	X		X		X			X	
Abbreviated Physical Examination ^e	X				X				
Vital Signs ^f	X	X	X	X	X		X	X	X
Adverse Events	X	X	X	X	X		X	X	X
Concomitant Medications	X	X	X	X	X		X	X	X
Hematology ^g	X	X	X	X	X		X	X	X
Serum Chemistry h	X		X		X			X	X
Urine Pregnancy Test i	X	X	X	X	X		X	X	X
Taste and Palatability Questionnaire with InClinic Dosing ^j	Performed on Day of Switch, and at the following two consecutive visits								
Transcranial Doppler k	Performed as standard of care								
Study Drug Dispensing and Accountability ¹	X	X	X	X	X	X	X	X	X

Abbreviations: CRF, case report form; EOS, End of Study; Q12Wk, every 12 weeks; Q24 Wk, every 24 weeks; Q48 Wk, every 48 weeks; TCD, transcranial Doppler.

Study Day/Week	Treatment Period					EOS			
	First 48 Weeks			After Week 48			+7 days ^c		
	Day 1 ^a	Week 12 b ± 5 days	Week 24 ± 10 days	Week 36 b ± 10 days	Week 48 ± 10 days	Q12Wk ± 10 days	Q24 Wk ± 10 days	Q48 Wk ± 10 days	

Voxelotor

GBT440-038

- a. Day 1 assessments will be performed prior to dosing. If any of the Day 1 assessments were performed at the last study visit in the originating (parent) clinical study, and the Day 1 visit occurs on the same date, the tests do not need to be repeated.
- b. Week 12 and Week 36 planned visits for participants who roll over to this study from Study GBT440-042 will be for drug dispensing, collection of adverse events and concomitant medications only.
- c. The EOS visit should be conducted 4 weeks (28 days) after the last dose of study drug (+7-day window).
- d. Height and weight will be collected only for participants < 18 years of age.
- e. Will include general appearance; examination of eyes, skin, cardiovascular system, and respiratory system; abdominal examination; and a symptom-directed examination.
- f. Heart rate and blood pressure will be measured after participant has rested for ≥ 5 minutes in the seated or supine position. If the first vital sign measurement is outside the normal range and deemed clinically significant, the measurement will be repeated within 5 minutes.

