- g. Will include the following: hematocrit, hemoglobin, mean corpuscular hemoglobin concentration, mean corpuscular volume, platelet count, red blood cell distribution width, reticulocytes (absolute and percent), and white blood cell count with differential.
- h. Will include the following: alanine aminotransferase, albumin, alkaline phosphatase, aspartate aminotransferase, bilirubin (total, direct, and indirect), blood urea nitrogen, creatinine, lactate dehydrogenase. Laboratory values for bicarbonate, calcium, chloride, glucose potassium, and sodium should only be recorded on the CRF if the laboratory value is abnormal and considered clinically significant by the Investigator).
- i. Will be performed for female participants of childbearing potential only. If the urine pregnancy test is positive, the result must be confirmed per local standard of care (eg, ultrasound or serum pregnancy test).
- j. Upon introduction of a new dosage form (either powder for oral suspension or dispersible tablets) or switch to higher dose (ie, modified dispersible tablet) to participants, a brief questionnaire will be administered to parents and/or children (aged ≥ 5 years) during the first visit when the transition is made and at the subsequent 2 scheduled visits.
- k. For all participants, results from TCD assessments performed as part of standard of care at each site will be recorded on the CRF.
- 1 Voxelotor will be dispensed in 12-week (~90-day) intervals with instruction to participants to return any used/unused bottles/stick packs to the clinic. At the Day 1 Visit, only study drug dispensing will be performed. At the EOS visit, only study drug accountability will be performed.

APPENDIX B. SCHEDULE OF ASSESSMENTS FOR SELECT SITES PARTICIPATING IN VOXELOTOR PLASMA AND WHOLE BLOOD PK COLLECTIONS UPON SWITCHING TO THE MODIFIED DOSE DISPERSIBLE TABLETS ^a

Study Day/Week	Day of Switch	14 Days Post-Switch	12 Weeks Post-Switch
PK Sample Collection (plasma and whole blood)	X	X	X
	(Predose)	(Predose)	(Predose)
Other Assessments	Per Scheduled Visit on Day of Switch (Appendix A) and must include Safety Assessments ^b Concomitant Medications Update	Safety Assessments ^b Concomitant Medications Update	Safety Assessments ^b Concomitant Medications Update
Taste and Palatability Questionnaire	X	X	X

Abbreviations: PK, pharmacokinetic.

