Note: The last dose of voxelotor should be taken 24 hours (\pm 1 hour) before PK sampling. The participant or their caregiver are to record the time of the voxelotor dose taken prior to each of these visits.

CONFIDENTIAL 58

^a Once the modified dose DT is available, switching to the modified dose DT will begin for subjects starting this study after completion of their parent study. For subjects that are already enrolled on this study, switching will begin at the subject's next scheduled visit (eg, Week 12, Week 24, etc.).

^b Safety assessments include AE and SAE monitoring, protocol-specified hematology and serum chemistry tests, abbreviated PEs, and protocol-specified vital sign measurements.

Appendix C. LIVER SAFETY: SUGGESTED ACTIONS AND FOLLOW-UP ASSESSMENTS [AND STUDY DRUG RECHALLENGE GUIDELINES]

This appendix is included to support Study transition to Pfizer Pharmacovigilance processes and systems.

Potential Cases of Drug-Induced Liver Injury

Humans exposed to a drug who show no sign of liver injury (as determined by elevations in transaminases) are termed "tolerators," while those who show transient liver injury but adapt are termed "adaptors." In some participants, transaminase elevations are a harbinger of a more serious potential outcome. These participants fail to adapt and therefore are "susceptible" to progressive and serious liver injury, commonly referred to as DILI. Participants who experience a transaminase elevation above 3 × the upper limit of normal (ULN) should be monitored more frequently to determine if they are "adaptors" or are "susceptible."

Liver function tests (LFTs) are not required as a routine safety monitoring procedure in this study. However, should an investigator deem it necessary to assess LFTs because a participant presents with clinical signs/symptoms, such LFT results should be managed and followed as described below.

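### After Week 48, children under 12 are weighed only every 48 weeks, so a weight-banded dose can lag a band change by up to 336 days (356 with visit windows)

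*Protocol*

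**What the plan says.** Protocol Section 5.1 gives everyone aged 12 or over 1500 mg whatever their weight. Children under 12 receive a weight-banded dose meant to match adult exposure at 1500 mg. On later changes it says: "The dose should be adjusted if the participant's weight increases or decreases at a scheduled clinic visit". The next sentence fixes when weight is known: "weight will be measured according to the Schedule of Assessments (Appendix A), and dose adjustments made as needed".

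In Appendix A the Weight and Height row is marked at Day 1, Week 24, Week 48 and Q48 Wk. It is blank at Week 12, Week 36, Q12Wk, Q24 Wk and End of Study. Note d limits the measurement by age: "Height and weight will be collected only for participants < 18 years of age". This covers every child under 12 but adds no time points.

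Visits do take place between weighings. After Week 48 the Q24 Wk visit carries vital signs, adverse events, concomitant medications, hematology and pregnancy testing. Drug supply is more frequent: "Voxelotor will be dispensed in 12-week (~90-day) intervals". Weight does not enter through vital signs, which Section 6.7 defines as blood pressure and heart rate.

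Table 2 in Section 5.1 sets higher weight-banded doses for the modified dispersible tablet. Under Appendix B, note a, children already enrolled change over at their "next scheduled visit (eg, Week 12, Week 24, etc".) Week 12 has no scheduled weight, and the safety assessments listed for the Day of Switch do not include one.

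**The concern.** The dosing rule works only as often as weight is measured. For the first 48 weeks that is every 24 weeks. From then on, in a study with no fixed treatment duration, it is every 48 weeks, and no reason is given for the change. A growing child can be seen at the clinic and resupplied several times while still on the dose for a lighter band, and nothing in the plan requires a weight that would show it.

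The bands exist to hold exposure near the adult level. A missed upward crossing leaves the child on a dose the protocol otherwise reserves for managing an adverse event, without an event behind it. SAP Section 8.2.1 summarises missed doses and dose reductions, and has no category for a dose that lags the child's band. The same gap works in reverse: a child who drops a band could remain on the higher dose.

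The switch to Table 2 is a second instance. It is the point at which the sponsor deliberately resets weight-based doses, and it can fall at a visit without a weight.

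**Working it through.** The documents state no maximum time on an outdated dose, so there is no plan figure to reproduce. The inputs are the visit intervals and windows in Appendix A (±5 days at Week 12, ±10 days at later treatment visits), the doses in Tables 1 and 2, and the reduction levels in Tables 3 and 4.

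**Gap between scheduled weights.** Gap = weeks × 7. With windows, add the days by which the first visit can be early and the second late.

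- Day 1 to Week 24: 24 × 7 = 168; 168 + 10 = 178 days.
- Week 24 to Week 48: 24 × 7 = 168; 168 + 10 + 10 = 188 days.
- After Week 48: 48 × 7 = 336; 336 + 10 + 10 = 356 days.

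The nominal gap therefore doubles after Week 48. If crossings are spread evenly over the interval, the average delay is 336 / 2 = 168 days.

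**Size of the dose step, same formulation.** Shortfall = 1 − dose held / dose assigned to the new band.

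| Crossing | Dosing table | Held (mg) | Assigned (mg) | Shortfall | Dose Reduction 1, new band (mg) |
|---|---|---|---|---|---|
| 10 kg | Table 1 | 400 | 600 | 1 − 400/600 = 33% | 400 (powder, Table 3) |
| 20 kg | Table 1 | 600 | 900 | 1 − 600/900 = 33% | 600 (powder, Table 3) |
| 10 kg | Table 2 | 500 | 800 | 1 − 500/800 = 37.5% | 500 (Table 4) |
| 20 kg | Table 2 | 800 | 1200 | 1 − 800/1200 = 33% | 900 (Table 4) |

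In three of the four rows the dose held equals Dose Reduction 1 for the correct band. In the fourth it is below it. The 40 kg step is left out because it also changes formulation, so the mg ratio is not like for like.

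**When the old dose becomes low by the protocol's own standard.** With mg/kg as a rough proxy for exposure, the least the new band accepts is its dose divided by its upper weight limit. The old dose falls below that at: weight = old dose / least accepted mg/kg.

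- Table 1, 10 to <20 kg: 600/20 = 30 mg/kg; 400/30 = 13.3 kg.
- Table 1, 20 to <40 kg: 900/40 = 22.5 mg/kg; 600/22.5 = 26.7 kg.
- Table 2, 10 to <20 kg: 800/20 = 40 mg/kg; 500/40 = 12.5 kg.
- Table 2, 20 to <40 kg: 1200/40 = 30 mg/kg; 800/30 = 26.7 kg.

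**Age of the weight at the Table 2 switch.**

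- At Week 12: 12 × 7 + 5 = 89 days at most.
- At a Q12Wk visit 36 weeks after the last weight: 36 × 7 = 252; 252 + 10 + 10 = 272 days.

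**After the change.**

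- Weight at each Q24 Wk visit: 24 × 7 = 168; 168 + 20 = 188 days.
- Weight at each dispensing visit: 12 × 7 = 84; 84 + 20 = 104 days.

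**The case against.** The strongest reply is that no loss of exposure has been shown. By the mg/kg proxy, a child must gain 25% to 33% beyond the crossing weight (10 to 12.5 or 13.3 kg; 20 to 26.7 kg) before leaving the range the new band already accepts. The 33% to 37.5% figures are steps in assigned mg between bands, not measured exposure deficits. This stands, and it limits the point. Without growth rates the number of children affected cannot be estimated.

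Second, 336 days is the worst case, and the exposed period ends at age 12, when the dose no longer depends on weight. Both are true.

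Third, sites may weigh children anyway. Protocol Section 6 allows extra assessments, but for adverse-event management or local standard of care, not for dosing. The blood-volume limit in Section 6.10.2 is per kg, so sites need some working weight when hematology is drawn, though not a fresh one. The Pharmacy Manual and the IRT manual are not available, so whether they ask for a weight at dispensing is unknown. The delay is therefore permitted, not inevitable.

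Fourth, SAP Section 8.2.6 groups weight with the vital signs to be summarised at every visit. That does not change the protocol schedule, which cannot supply those values; if anything it favours the fix.

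Fifth, the Week 12 switch example is weak. A weight at most 89 days old is fresher than either proposed schedule guarantees, children entering the study after the modified tablet is available switch from Day 1, and moving to Table 2 on an old weight carries the existing band error forward without adding one. This is fair. The switch matters mainly at later visits, and the main point does not depend on it.

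**Conclusion.** The concern holds. Section 5.1 and Appendix A do not contradict each other, because the first defers to the second, but the schedule is too sparse for the rule it serves. After Week 48 the longest scheduled gap between weights is 336 days (356 with windows), against 168 (188) between Weeks 24 and 48. The average delay is about 168 days, assuming crossings evenly spread over the interval. At the 10 kg and 20 kg crossings the child holds a dose 33% to 37.5% below the assigned mg amount, at or below Dose Reduction 1 for the correct band.

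The schedule facts and the arithmetic are certain. The clinical effect is less so: modest near a boundary, dependent on mg/kg as a rough proxy, and of unknown frequency. The study's analyses are descriptive, and no planned result is shown to be compromised. The change is worth making because it makes the protocol's own dosing rule workable at very little cost.

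**What to change.** In Appendix A, for participants under 12 years:

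- Mark weight at the Q24 Wk visit, which brings the longest gap to 188 days with windows.
- Preferably mark it at every dispensing visit (Week 12, Week 36 and Q12Wk as well), which brings it to 104 days.
- Require a weight on the Day of Switch to Table 2 doses at all sites, not only those collecting pharmacokinetic samples, so that the new dose is chosen from a same-day weight.

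The cost is a schedule edit and one extra weighing and data entry at visits that already take place. Note b restricts Weeks 12 and 36 to dispensing, adverse events and concomitant medications for participants from Study GBT440-042. It needs a matching edit if any of them are under 12.
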